### • Drug Abuse Screening Test-10 item (DAST)

The AUDIT is part of the NIDA CTN Common Data Elements for use in clinical trials. The DAST is a 10-item brief, self-report instrument for population screening, clinical case finding and treatment evaluation research. It can be used with adults and older youth. The DAST-10 yields a quantitative index of the degree of consequences related to drug abuse. The instrument takes approximately 5 minutes to administer and may be given in either a self-report or interview format. The DAST may be used in a variety of settings to provide a quick index of drug abuse problems. It will be evaluated continuously and as a categorical outcome (yes/no).

### Secondary outcomes:

### • Beck hopelessness inventory

This twenty-item measure has been widely used to assess hopelessness through a series of true/false statements (1, 0) that create a sum score.

### • PROMIS – anxiety

This clinically valid, 7 item measure has been developed as part of the National Institute of Health (NIH) toolkit to assess anxiety in individuals 18 and older. Endpoints range from 1=never to 5=always. It can be used as a sum score and categorizes responses as "none to slight", "mild", "moderate," and "severe".

### • PROMIS - depression

This clinically valid, 8 item measure has been developed as part of the NIH toolkit to assess depression in the past two weeks. It assesses symptoms ranging from 1=never to 5=always and can be used in individuals 18 and older. It can be used as a sum score and categorizes responses as "none to slight", "mild", "moderate," and "severe".

#### • PROMIS – loneliness

This clinically valid, five item measure was developed as part of the NIH toolkit to assesses feelings of social isolation on a five-point scale from 1=never to 5=not at all.

#### Mediators & additional outcomes

• Self Compassion Scale (SCS)

This twelve-item scale assesses self compassion on a scale of 1=almost never to 5=almost always. Items will be summed and used as a continuous measure.

• Difficulties in Emotion Regulation Scale

This 18-item scale assesses emotion dysregulation on a scale from 1=almost never (0-10%) to 5=almost always (91-100%). It can be summed up (several items reverse coded) and also has six subscales: Nonacceptance of emotional responses, difficulty engaging in goal-directed behavior, impulse control difficulties, lack of emotional awareness, limited access to emotion regulation strategies, and lack of emotional clarity.

• Mindful Attention Awareness Scale

This is a 15-item scale that assesses mindfulness on a scale of 1=almost always to 6=almost never. It is summed and used as a continuous measure.

Moral Injury and Distress Scale

This six item scale measures moral injury on a scale from 0=not at all to 4=extremely. It is coded categorically (yes moral injury=1, no moral injury=0) and as a continuous outcome.

• Craving

Craving will be measured for alcohol, opioids, methamphetamine, marijuana, psychedelics or other substances (provide name) from 0=no craving at all to 100=maximum possible.

• Trauma-related Shame Inventory

This 24-item measure assesses trauma-related shame from 0=not true of me to 4=completely true for me. It is summed and analyzed as a continuous outcome.

#### Covariates:

• Negative life events

This measure assesses exposure to 31 possible negative life events and assesses if they occurred before age 18, after age 18 or in the past year. Seven additional adverse childhood experiences will also be specifically assessed.

- Interpersonal Violence Short Form/Revised Conflicts Tactics -Short form
  This twenty-item measure is designed to capture intimate partner
  violence. Specifically, it assesses three tactics used when there is
  conflict in the relationships of dating, cohabiting, or marital couples:
  Negotiation, Physical Assault, and Psychological Aggression.
  Questions are answered in terms of frequency of occurrence.
  Scoring can occur in a variety of ways as outlined here
- Demographics

### **Subsection 2.8 - Phase II MSC Intervention**

(MSC) is a mind-body integrative health intervention that utilizes meditations, other contemplative practices, home practices, and experiential exercises (including group

discussions) to increase SC. MSC can be done in groups of 10-25. To increase feasibility of MSC for use in RDTSs, we will aim to adapt MSC to 7 sessions (6 weekly sessions in alignment with the MSC short course plus the half day retreat included in the full course to facilitate skill consolidation). Sessions will be conducted in a group-based format: prior research found group-based formats equivalent to individual-level interventions for PTSD/SUD.

#### The MSC sessions are as follows:

#### **Session 1:** What is MSC?

- o **Topics:** Why am I here? How to approach MSC. Guiding Principles. 3 components of SC. Misgivings.
- o **Key Practices for PTSD/SUD:** How do I treat a friend? Physiology of SC and Criticism SC Break. Informal Practice: SC Bracelets

### **Session 2:** Practicing SC

- o **Topics:** "Resistance & backdraft". How we cause ourselves unnecessary suffering. Development of Safety & Trust. Inner Ally
- o **Key Practices:** Affectionate Breathing. Practicing Loving Kindness. Soles of the Feet. Mindfulness & SC in Daily Life. Here and Now Stone.

### Session 3: Discovering Your Compassionate Voice

- o **Topics:** Self Criticism & Safety. Core Values. Compassionate Conversations with Self.
- o **Key Practices:** Meeting the Inner Critic. Finding Phrases. Compassionate Letter to Ourselves.

### Session 4: SC & Resilience

- o **Topics:** Applying SC to Difficult Emotions. Hidden Values in Suffering. Emotion of Shame Described & Demystified.
- o **Key Practices:** Core Values Exercise. Living with a Vow. Silver Linings.

### **Session 5:** Meeting Difficult Emotions

- o **Topics:** Self-forgiveness. Challenging Relationships.
- o **Key Practices:** Compassionate Friend. Meeting Unmet Needs. SC Break in Relationships. SC with Equanimity.

#### **Living Deeply Half-Day Retreat:**

o **Key Practices:** Soft Soothe Allow. Affectionate Breathing. Compassionate Movement.

### **Session 6:** Making it Count

- o **Topics:** Integrate Positive Psychology. Concepts of Savoring, Gratitude, Self-Appreciation. Tips for Maintaining Practice.
- o **Key Practices:** Savoring. Gratitude. Self-Appreciation.

#### **Subsection 2.9 - Phase II Treatment as Usual**

Selecting appropriate attention control groups for behavioral intervention research, particularly for mindfulness-based interventions, can be problematic. Comparator groups often also improve as they tend to target related mechanisms (e.g., social support, health behaviors, improved attention). After weighing the pros and cons, a "treatment as usual" (TAU) approach was selected, whereby the MSC will be compared to TAU at the RDTS. However, to control for the confound of weekly compensation, TAU participants will meet with study staff seven times over the 6-week period and fill out short psychosocial surveys on non-distressing topics (e.g., personality tests, attitudes surveys) in exchange for compensation commensurate with the MSC group. We believe this will also help with retention of the TAU group over time and strike an appropriate balance between controlling for the effects of study participation while minimizing confounds that often occur with active control groups in behavioral interventions.

#### **Subsection 2.10 - Phase II Post Assessment**

After the seventh session (of either MSC or TAU), a post-assessment will be administered via tablet.

### Assessments (see detailed description above)

### Primary outcomes:

- PTSD PCL-5 (lifetime, past year):
- Substance use AUDIT DAST

#### Secondary outcomes:

- Beck hopelessness inventory
- PROMIS anxiety
- PROMIS depression
- PROMIS loneliness

#### Mediators & additional outcomes

- Self Compassion Scale (SCS)
- Difficulties in Emotion Regulation Scale
- Mindful Attention Awareness Scale
- Moral Injury and Distress Scale
- Craving
- Trauma-related Shame

#### Covariates:

- Negative life events (updated)
- Interpersonal Violence Short Form
- Demographics

Women in the MSC group will also be invited to participate in-depth, semi-structured interviews (approximately 20 minutes in length) to share their experiences with the intervention. They will be compensated \$10 for the interview.

### **Refusal Subsection 2.11 - Phase II Dealing with Program Attrition**

Based on the team's prior research, we conservatively estimate 80% retention over time for a target enrollment of 202, for a total of 8 cohorts of 24-26 participants (divided equally into two groups per cohort). In the team's prior work, 82% of those screened were eligible for participation: thus, we will aim to screen 246 WEH.

We will work hard to ensure retention of participants during the study. The Locator Guide is key to maintaining effective follow-up. RAs, GSRs, and the PI will work to ensure maximum retention.

### **Subsection 2.12 - Phase II Follow-up**

At four-month follow-up, we will contact the women with assistance from the site supervisor or by using our Locator Guide. These sessions will occur in person (at a private location convenient for the participant) or over Zoom on an encrypted UCLA device as requested by the participant.

### **Subsection 2.13 - Phase II Compensation**

The Phase II compensation is listed below. Each participant will receive a total of up to \$150 over the course of the study.

- \$5 screener (after completing screener)
- \$15 baseline measures (after completing)
- \$10 per session in the intervention (at the end of each session; for a total of 7 sessions)
- \$20 immediate post-intervention follow-up measures (after the final session)
- \*\$10 if they complete an additional qualitative interview
- \$30 4-month follow-up (after completion)

Both the MSC and TAU groups will receive a certificate of completion at the end of the 6-week (7 session) program.

### **Subsection 2.14 - Program Fidelity**

To ensure program fidelity, all procedures will be closely supervised by the PI, [name]. Detailed training materials will be provided to all staff, and staff will be required to complete a quiz prior to working on site. For those involved in administering the interventions, a detailed teachers manual will be provided, and all staff will be expected to adhere to the manual, with some flexibility allowed depending on the needs of the group, as is typical with MSC programs. All trainers will be certified in MSC and have an interest in working with unhoused persons.

### **Subsection 2.15 - Research Staff Competencies & Training**

UCLA has implemented an educational program on the protection of human research

subjects. All study personnel who are responsible for the design and conduct of this project must complete the Collaborative Institutional Training Initiative Human Research Curriculum (CITI program), with the confirmation of completion of the training on file. The following courses should be completed by all staff prior to engaging in study activities.

- Human Research Social & Behavioral Researchers & Staff
- Good Clinical Practices (GCP) courses (mandatory for RAs & GSRs)
- Refresher courses are also available on CITI website

https://about.citiprogram.org/en/homepage/) as needed.

Further, all research staff will be highly trained by the PI in the following:

- Trained in specific protocols for dealing with emotional and mental distress (e.g., remaining calm, immediately finding appropriate onsite clinical staff).
- Trained in observational and communication skills, and in providing psychosocial support, particularly as it relates to emotional and information support.
- Trained in the California Mandatory Reporting Laws governing reporting of child abuse, domestic violence, and elder/dependent abuse. Protocols governing reports to the California Department of Family and Child Protective Services, or (in the case of domestic violence) local police, will be carefully followed. Study participants will receive full disclosure regarding mandatory reporting laws during the informed consent process and discussion of confidentiality. In terms of current or recent abuse experience, research staff will refer the participants to the onsite Prototypes clinical staff.
- Trained in our "RED FLAG" protocol and in reporting adverse events. Any adverse event will be documented in REDCap and reported to the IRB if appropriate.
- During research study training, the research team will be supervised by the PI as they practice the scripts for the screener, psychosocial questionnaires, and collecting data using REDCap.

### Subsection 2.16 - Data Entry, Management, & Confidentiality

In Phase 2, secure and encrypted platforms will be used:

- **REDCap:** Interview data will be captured electronically using REDCap (Research Electronic Data Capture; http://project-redcap.org/), a secure, web-based application designed to support data entry and storage for research studies. Participants will answer surveys via an electronic tablet and the data will be uploaded in real-time. Possible errors, including incomplete responses, logic checks, and data range checks will be flagged by the RedCap software during input so that they can be corrected immediately.
- The GSRs, as supervised by [name], will routinely check to ensure data is accurately entered.

### Procedures to safeguard confidentiality

Confidentiality of data will be protected by use of subject code on all data and questionnaires.

Any forms that link participant with their codes will be stored electronically on UCLA's secure server and only senior research staff and the PI will have access. All self-report data will be immediately uploaded onto UCLA's secure server via REDCap.

- Participants will be reminded that their interview questions will be provided over a tablet that will immediately transfer the data to the UCLA secure server and site staff will not see their data.
- We will minimize the risk by strictly adhering to confidentiality procedures. All study staff will be rigorously trained in methods to promote confidentiality. The staff will also be taught to treat participants in a non-judgmental, professional and confidential manner.
- Confidentiality of data will be protected by use of subject code on all data and questionnaires. Data including subject identifiable information (eg: locator form etc) will be linked to a code on REDCap for access in real time to track participants and only research staff will have access. REDCap also allows for participant's names and IDs to be viewed without access to their responses to the other items in the survey. Tracking of participants for their follow-ups will be based upon the information the participant reveals on their Locator Guide. When contacting people over the phone, we will use their preferred method and the research staff will identify themselves per participants' wishes.
- To protect confidentiality and reassure subjects, the research staff will be providing explicit explanations in the beginning of the program that they will share no confidential information. The trained research staff will administer the questionnaires individually to the participants.
- Subject identifiable data will be destroyed upon completion of the study. All the data will be stripped off any identifiable information and only de-identified database will be kept for analysis and dissemination.

### **Subsection 2.17 - Using REDCap**

- For electronic data electronic data entry, log onto REDCap with you user ID and password: (https://gpsslvpn.mednet.ucla.edu/https/ctrcapps.medsch.ucla.edu/redcap/)
  - RedCap also incorporates suitable validity checks at the point of data entry to prevent "out of range," "missing" or other checkable data entry errors.

### **Subsection 2.18 - Data Security**

- All questionnaires must be identified by a code number (Study ID) only and patient identifier information will also be linked on REDCap through this code.
- The informed consent with the participants' names and signature will be on REDCap.

- All databases are accessible only to key investigators and research assistants on the project though password-protected login. Each member of the research team has their own personal password and login (administered through UCLA Mednet).
- The electronic data files are stored on the secure, password-protected UCLA server.
- This data is available for access on the UCLA server to authorized users through a password-protected web application.
- Authorized users can export deidentified data into Excel or other statistical software sheets for further analyses.
- The de-identified database will be archived for future analyses and all other identifying data will be destroyed at the end of the study.

#### **Subsection 2.19 - Post Data Collection**

- Validity checks on REDCap will be done right after any interview or other data collection is completed.
- Routine statistical validity checks should identify missing or suspect entries at agreed defined intervals (twice per month or as needed) by approved study staff, so that correct data can be obtained from the research staff, participants or their records if needed.
- Thorough data cleaning should be performed before any data analysis.

### **Subsection 2.20 - End of Study**

- De-identified electronic data will be maintained for the period agreed in the study protocol (indefinitely).
- Final cleaned electronic data will be used for all statistical analyses.

# Section 3 – Data analytic plan

• *Power analysis*. Sample size was estimated using G\*Power and standard guidelines for testing mediation,  with α=.05, β=.80, and the standard deviation bound at ±1.91. Effect size estimates were derived from prior research on SC interventions for PTSD, which found a small-medium effect size (Cohen's d=0.2-0.5).  Particularly since the effect of MSC to reduce PTSD symptoms is emerging research, findings have been mixed regarding effect sizes for direct and indirect effects of SC interventions on PTSD, with some studies finding large effects of reduced PTSD due to SC interventions,  and others finding medium effect sizes.  (Of note, few randomized trials have been conducted).  To account for additional covariates, the clustering design,  and Type 1 error due to multiple tests, a small-medium effect size of .3 was conservatively estimated. Sample size appropriate for mediation was derived from a percentile bootstrap method, which simulations consistently show to be the most powerful test compared to similar methods (e.g., Sobel, bias-corrected bootstrap).  This yielded a final sample size of 162. Based on the team's prior research, we conservatively estimate 80% retention over time for a target enrollment of 202, for a total of 8 cohorts of 24-26 participants (divided equally into two groups per cohort). In the

team's prior work, 82% of those screened were eligible for participation: thus, we will aim to screen 246 WEH.

- Statistical analysis. Initial analysis will include descriptive statistics. Data will be screened for outliers and deviations from normality; results will be considered in subsequent analyses. Patterns of missing data will be examined using logistic regression (0=missing; 1=complete) and will be reported in results. Based on prior research, very little missing data on key independent or dependent variables is expected. Any missing data on independent variables or continuous dependent variables will be imputed using multiple imputation and related methods. Although cohorts should be comparable in terms of demographics (e.g., age, ethnicity) and other risk factors (e.g., type of drug use, history of recidivism), propensity score methods and/or multilevel analyses (with cohort/cluster as a random effect) will be utilized to account for these or any other covariates statistically different between cohorts at baseline. Reliability for computed scores will be assessed using Cronbach's alpha. Next, a series of t-tests and chi-squares will examine differences between groups (MSC vs. TAU). Then, for each dependent variable of interest, key predictors and covariates will be examined using a series of t-tests, chi-squares, and ordinary least squares (for continuous outcomes) and logistic (for dichotomous outcomes) bivariate regression models. Type, timing and amount of trauma exposure will be examined as covariates, given their link with PTSD incidence, severity,  substance use,  and distress.
- To evaluate reductions in PTSD symptoms, first, treatment response ( $\geq$  5-point reduction in symptoms) and clinically meaningful improvement (≥ 10-point reduction in symptoms) will be calculated for both immediate and 4-month follow-up. Potential covariates (e.g., demographic indicators; type, timing and amount of trauma exposure, including history of incarceration) will be screened for inclusion (included if p<.05). Change over time will be analyzed, using data from the three time points, using a mixed-effects repeated measures approach. This will also allow for a test of fixed (e.g., treatment group) and random (e.g., cohort) effects over time and conserves power by capitalizing on the longitudinal design. Reductions in PTSD will be examined using a modified Poisson distribution with robust variance, which tends to be less biased than a logit-based approach. Reductions in symptoms (measured continuously) will also be evaluated using a Gaussian distribution. Substance use will be evaluated using the TLFB, quantified as time to first use, days of use and relapse status (abstinent [did not use], lapse [used after study intervention but did not revert to regular use], or relapse [used substances for more than one third of days]). 34,35 Group x time contrasts will be tested. Identical analytic approaches will be used to examine secondary outcomes (suicidality, depression, and anxiety).
- To test for mediation effects, AGReMA (A Guideline for Reporting Mediation Analyses of Randomized Trials and Observational Studies) will be followed. A series of longitudinal structural equation models (SEM) will examine both direct and indirect effects by which change in mediators (emotion regulation, trauma-related guilt, trauma-related shame, moral injury and craving) are associated with change in PTSD, substance use, and secondary outcomes over time. Confidence intervals for indirect effects will be obtained through percentile bootstrap. SEM has the capacity to test for bidirectional

effects between PTSD symptoms and substance use. Model fit (e.g., Root Mean Square Error of Approximation) will be compared to find hypothesized paths that best fit the data.

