#### **Assessments**

#### Primary outcomes:

• PTSD PCL-5 (lifetime, past year)

PTSD symptoms will be measured using the PTSD Checklist for DSM-5 (PCL-5),  $^{1,2}$  which will be scored continuously and according to diagnostic criteria. The PCL-5 initially starts with the identification of the presence of exposure to a DSM-V traumatic event; assesses actual or threatened death, serious injury or sexual violence; and whether the person directly experienced it. Twenty additional items assess all four B-E criteria (re-experiencing, avoidance, negative thoughts or cognitions, hyperarousal), assessed on a Likert-type scale from 0 (not at all) to 4 (extremely). Treatment response will be defined as a  $\geq$  5-point reduction in symptoms and clinically meaningful improvement as  $\geq$  10-point reduction in symptoms. PTSD will be assessed for worse lifetime event and (if applicable) worst event in the past year.

Alcohol Use Disorders Identification Test (AUDIT)
 The AUDIT is part of the National Institute on Drug Abuse (NIDA)
 Clinical Trials Network (CTN) Common Data Elements for use in

clinical trials. The Audit is a 10-item alcohol screen that helps identify persons who are hazardous drinkers or who have active alcohol use disorders. It can be calculated as a sum score and will be analyzed as a continuous and categorical (yes/no used alcohol) outcome.

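### The power paragraph's inputs (SD of ±1.91, effect .3, power .80, N=162) do not fit together for the MSC versus TAU comparison of PTSD, where power at d=.3 is about .48

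*Combined protocol and SAP*

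**What the plan says.** The power analysis in Section 3 sets its inputs "with α=.05, β=.80", "and the standard deviation bound at ±1.91". No variable, unit or source is given for the SD. Prior research on self-compassion interventions for PTSD is cited, "which found a small-medium effect size (Cohen's d=0.2-0.5", and after allowing for covariates, clustering and multiple tests "a small-medium effect size of .3 was conservatively estimated". The paragraph continues: "Sample size appropriate for mediation was derived from a percentile bootstrap method". The result is 162, raised to 202 enrolled for 80% retention. No path values, sidedness, intracluster correlation or PCL-5 standard deviation are given.

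Subsection 2.7 defines the PTSD outcome as the PCL-5: "Twenty additional items assess all four B-E criteria (re-experiencing, avoidance, negative thoughts or cognitions, hyperarousal), assessed on a Likert-type scale from 0" to 4. A fall of at least 5 points counts as treatment response. Section 3 repeats this and adds that "clinically meaningful improvement (≥ 10-point reduction in symptoms) will be calculated for both immediate and 4-month follow-up". The Statistical analysis text plans t-tests of MSC against TAU, a mixed-effects repeated-measures model over three time points, and group-by-time contrasts.

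**The concern.** Two things do not fit. First, an SD of 1.91 is very small for a 0 to 80 scale on which the plan treats 5 points as the smallest change worth calling a response. Second, an effect of .3 with 162 people in two equal arms is well short of what a two-group comparison needs for power .80.

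The power paragraph is the only place where the plan says what the trial can detect. If the .80 is read as applying to the PTSD treatment effect, a null result will be given more weight than the design supports. Nor can a reader find out what between-arm difference in PCL-5 points the trial is able to detect.

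**Working it through.** **Inputs.** From Section 3: alpha .05 (sidedness not stated); "with α=.05, β=.80", where β is read as power, since a literal type II error of .80 would need only about 58 people; effect .3; 162 completers; 80% retention; 82% of those screened eligible. From Subsection 2.1: 1:1 allocation, so 81 completers per arm, and 8 cohorts. From Subsection 2.7: 20 items scored 0 to 4, so a total of 0 to 80.

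**1. The plan's own figures.** Retention and screening reproduce: 162/.80 = 202.5 (202 stated) and 202/.82 = 246.3 (246 stated). The 162 does not reproduce from the printed inputs. A two-group test at d=.3 and power .80 needs 176 per arm, 352 in total, two-sided (exact t), or 276 to 278 one-sided. A raw difference of .3 with SD 1.91 needs 637 per arm, 1,274 in total.

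**2. Is 1.91 a possible PCL-5 SD?** If scores were roughly normal, 95% would lie within ±1.96 × 1.91 = ±3.7 points of the mean on an 80-point scale. The 5-point response threshold would be 5/1.91 = 2.6 SDs. Neither is credible for this scale.

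**3. A numerical coincidence.** The noncentrality of a two-group t-test is d × √(n/2), with n per arm: .3 × √(81/2) = 1.909. A total of 160 gives 1.90 and 164 gives 1.92.

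**4. Power for MSC versus TAU.** At noncentrality 1.909 on 160 degrees of freedom, two-sided power is .475 by exact t (.48 by the normal approximation); one-sided it is .60. The effect detectable with power .80 at 81 per arm is d = .443 two-sided.

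**5. The mediation route.** Percentile-bootstrap power for an indirect effect was simulated at N=162 (600 replicates, 500 resamples, Monte Carlo error about ±.02; no direct effect, residual SD 1):

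| Assumed paths | Power |
|---|---|
| Both .26, exposure with SD 1 | .805 |
| Both .30, exposure with SD 1 | .92 |
| Two-arm exposure shifting the mediator by d=.3, second path .3 | .47 |
| The same, second path .5 | .49 |

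The value that gives .80 is .26, which the plan does not state. A 1:1 arm indicator has SD .5, so a first path of .26 per SD is a between-arm shift in the mediator of .26/.5 = .52 residual SDs, well above .3.

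**6. Adjustment and clustering** (assumed values; the documents give none). Baseline adjustment divides the noncentrality by √(1 − r²). At r=.5, 1.909/.866 = 2.20 and power is about .59; at r=.7, 1.909/.714 = 2.67 and power is about .76. In the other direction, the design effect with about 20 analysed per cohort (162/8 = 20.25) is 1 + 19.25 × ICC. At ICC .01, .02 and .05 it is 1.19, 1.39 and 1.96, and unadjusted power is about .42, .37 and .28, before allowing for there being only 8 clusters.

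**7. In PCL-5 points.** No SD is given, so 10 to 20 is assumed. Then d=.3 is 3.0 to 6.0 points, and the difference detectable with power .80 is .443 × 10 = 4.4 to .443 × 20 = 8.9 points, individual level and unadjusted.

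**The case against.** The strongest reply is that the paragraph sizes a mediation test, not a t-test, so t-test power of .48 does not refute the .80. That stands in part. A mediation calculation can arrive at 162 with power near .80, and 162 itself is not shown to be wrong. But none of the mediation readings tried gives .80 at the printed .3, and power for an indirect effect is not power for the PTSD difference between arms, which the plan tests and for which it states no other power.

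The second reply is that the planned repeated-measures model gains power over a single-time-point test. It may, as step 6 shows, but the plan states no correlation from which the gain could be computed. Even an assumed .7 leaves power below .80 before any cohort effect.

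A reader might also infer more than the documents support:

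- **That the trial claims to detect about half a PCL-5 point** (.3 × 1.91 = 0.57). The plan states no raw difference and never links 1.91 to the PCL-5. A standardised effect needs no SD, so no such target is printed.
- **That 1.91 is a mislabelled noncentrality.** The match is to two decimals and specific to N=162, but the plan does not mention noncentrality. The origin is inferred only, and the case for correction does not depend on it.
- **That the detectable difference should be judged against the 5- and 10-point thresholds.** These are reductions in symptoms that define response and improvement. They are not differences between arm means.

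**Conclusion.** The printed inputs are wrong as a set for the treatment comparison. An SD of 1.91 cannot describe the PCL-5 and belongs to no named variable. At d=.3 and 81 completers per arm, power for MSC versus TAU is about .48 two-sided, and .80 holds only from d of about .44. These figures rest on an unadjusted, individual-level two-group test at one time point. Baseline or repeated-measures adjustment would raise them and clustering would lower them, by amounts that cannot be fixed from the documents. The translation to 4.4 to 8.9 points depends wholly on the assumed SD of 10 to 20. The finding does not show that the sample size must change, nor how 1.91 arose.

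**What to change.** Revise the power analysis in Section 3, with N unchanged:

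1. Remove ±1.91 as an SD, or replace it with the correct quantity, naming its variable and source.
2. Limit the .80 statement to the mediation test, and state the path values and sidedness that it assumes.
3. State the power for the MSC versus TAU comparison of the PCL-5 at 162 completers: about .48 at d=.3, or .80 only at d of about .44, individual level and unadjusted. If adjustment or clustering is used, state the baseline correlation and cohort effect assumed.
4. Give the detectable between-arm difference in PCL-5 points for a stated SD or range of SDs.

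This costs a few sentences and changes nothing in enrolment or conduct. The drawback is that the stated sensitivity becomes less favourable.
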